Pre-post intervention and follow-up questionnaires will be self-completed by participants online via the survey platform Qualtrics, which will be linked to Prolific. Three short scales will be used to measure trait outcomes of mental health, wellbeing and sleep-related impairment at these timepoints (baseline/pre-intervention, post-intervention, three-week follow-up): the Depression Anxiety Stress Scale (DASS-21) (Lovibond, & Lovibond, 1995), Short Warwick-Edinburgh Mental Wellbeing Scale (SWEMWBS) (Ng Fat et al., 2017), and PROMIS Item Bank v. 1.0 - Sleep-Related Impairment - Short Form 4a (PROMIS-4a) (Hanish, Lin-Dyken & Han, 2017). The primary outcome will be stress (measured using the DASS-21 stress subscale), and the primary timepoint will be post-intervention (three weeks

post-randomisation). The secondary outcomes will include: anxiety and depression (from DASS-21), mental wellbeing (SWEMWBS) and sleep-related impairment (PROMIS-4a). State measures of positive and negative affect using the Positive and Negative Affect Schedule (PANAS-20) (Watson, Clark & Tellegen, 1988) (secondary outcomes) will also be completed during the baseline survey. Immediately after starting the breathwork (first session of breathwork), participants will be asked about the credibility and expectancy of the intervention randomly allocated to them to assess if the intervention and placebo are seen as equally credible and thus merit equal expectation of benefit. This will be measured using the Credibility/Expectancy Questionnaire (CEQ-6), which is another secondary outcome. The PANAS-20 will also be completed once at this timepoint, to gauge a sense of state change due to the breathwork, in addition to once more at post-intervention. The last secondary outcomes, which will be measured post-intervention, are: negative side effects (to judge the safety and tolerability profile of the breathwork) and adherence to protocol (number of times participants self-reported practicing breathwork out of the 21 days assigned). Other outcomes include general sentiment towards the protocol (i.e., positive, negative, neutral) and open-ended questions on participants overall experiences of the protocol and/or study period. Pre-intervention, simple demographics (Age, Gender and Ethnicity) will be collected and, at follow-up, participants will be asked if they can guess which condition they were allocated to (to tentatively see if blinding was successful—see Procedure section).

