Primary outcome measure

1. Subjective stress (DASS-21 stress subscale)

Secondary outcome measures:

2. Subjective anxiety (DASS-21 anxiety subscale)
3. Subjective depressive symptoms (DASS-21 depression subscale)
4. Subjective mental wellbeing (SWEMWBS)
5. Subjective sleep-related impairment (PROMIS-4a)

[All of above outcomes measured pre-post-follow-up]

6. Subjective positive affect (PANAS-20 positive affect subscale). Measured pre-intervention, after first breathwork session, and post-intervention.
7. Subjective negative affect (PANAS-20 negative affect subscale). Measured pre-intervention, after first breathwork session, and post-intervention.
8. Self-reported credibility and expectancy of protocol (CEQ-6). Measured after completing first session of breathwork.
9. Negative side effects due to protocol (whether participants experienced unpleasant/unwanted a) short-term effects, and/or b) lasting bad effects from the breathwork, to gauge safety and tolerability). Measured post-intervention.
10. Self-reported adherence to breathwork protocol (number of sessions participants self-report practicing out of 21 days assigned). Measured post-intervention.

Other—Overall experience, Hypothesis guessing, Attention checks

Optional questions on participants' perspectives and overall experience of the protocol (post-intervention) / study-period (follow-up), and if they can correctly guess which condition they were allocated to (follow-up). Lastly, The DASS-21, SWEMWBS, PROMIS-4a, and PANAS-20 will all have one attention-check question in them to ensure participants are completing the surveys properly.

Procedure

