Participants in the intervention group will be randomised to a guided audio of HVBR pre-recorded by a trained breathwork facilitator for ~20min/day over 21 days (three weeks). This will be delivered remotely online through audio link, and comprises evocative music and four rounds of hyperventilation with four separate retentions (breath holds), progressively increasing in length (from ~45seconds up to ~90 seconds). The average number of HVBR rounds used is usually 3-4, so four rounds were chosen for the intervention group. The duration of ~20min was deemed as a manageable time for participants, and several studies (ranging from days to weeks) on meditation have shown benefit can be derived from this low-to-moderate length of practice.

Participants in the control group will be randomised to a guided audio of placebo 'sham' HVBR pre-recorded by a trained breathwork facilitator for ~20min/day over three weeks. This will be delivered remotely through audio link, comprising music and four rounds of paced breathing at 15b/min (equal inhale:exhale without pauses) with four separate (shorter) retentions, slightly increasing in length (from ~10secs to ~25secs). The metric of 15b/min is in line with guidance from the British Journal of Nursing, Royal College of Physicians, and Johns Hopkins University which state that the average, healthy rate should range from: 12-18, 12- 20, and 12-16b/min, respectively.

Randomisation & blinding

The type of study is participant blinded RCT with assessor blinded data collection (that is, assessor is not present for data collection which is self-completed by the participant on a survey software platform). After completing the pre-intervention survey, participants will be

randomly assigned, via the online survey software Qualtrics using block randomisation (1:1), to receive either the intervention (HVBR), or placebo (15b/min). Participants will be blinded to their intervention (concealment)—the study is referred to as the Sussex Fast Breathwork Study and the technique of breathwork will be referred to as 'rhythmic breathing' in both the active intervention and placebo control breathwork audios, in an attempt to blind participants to the intervention being used.

Safety & ethical considerations

This study has been approved by the Research Ethics Committee at the University of Sussex Sciences & Technology C-REC (reference: ER/GF221/5).

References

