the imputation model, and used for sensitivity analysis. Analysis without baseline covariates will be included as sensitivity analysis. If a participant answers more than one of the attention-items incorrectly at each timepoint their data will be excluded from the main analyses but included in a sensitivity analysis.

Exploratory analysis of secondary measures

Adherence to breathwork protocol

Post-intervention, participants will answer how many times they completed the guided breathwork out of the assigned 21 days. This will be compared between groups via unpaired t-test, and correlated with outcome scale scores on DASS-21, SWEMWBS, PROMIS-4a and PANAS-20 within each condition to see whether there are any associations between adherence and changes in these scale scores. Adherence will be looked at as a moderator.

Credibility & expectancy of breathwork protocol

CEQ-6 scores will be compared between groups via unpaired t-tests. If there are significant differences between groups on credibility/expectancy, primary tests will be run again with this used in covariance analysis. Similar to adherence, CEQ-6 scores will be correlated with the outcome scale scores above, to see whether there are relationships between CEQ-6 and changes in these scale scores within each condition.

Negative side effects due to protocol

Whether participants experienced: 1) Unpleasant/unwanted short-term effects and/or 2) Lasting bad effects from the breathwork. Analysis will be content analysis.

Other outcomes (qualitative)

Below outcomes will be explored to offer complementary findings to main quantitative analyses above.

Overall Experience

Participants' perspectives and overall experience of the breathwork protocol and study-period (i.e., positive, negative, neutral, general notes, etc.) post-intervention and follow-up. At post-intervention, analysis will be sentiment analysis, based on whether a participant reported their overall experience of the breathwork as strongly positive, positive, neutral, negative, or strongly negative.

Hypothesis Guessing

Whether participants can correctly guess which condition they were allocated to, at end of follow-up questionnaire, to tentatively infer if blinding was successful.

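### Negative effects are asked about only at post-intervention, not in the existing three-week follow-up survey, and no between-arm difference or interval is planned for them

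*Protocol*

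**What the plan says.** The Protocol's Outcome measures section introduces the outcome thus: "The last secondary outcomes, which will be measured post-intervention, are: negative side effects (to judge the safety and tolerability profile of the breathwork". Item 9 of the secondary outcome list has two parts, short-term and lasting effects, and gives the same single timepoint: "b) lasting bad effects from the breathwork, to gauge safety and tolerability). Measured post-intervention". Items 1 to 5 (the three DASS-21 subscales, SWEMWBS and PROMIS-4a) carry a different note: "All of above outcomes measured pre-post-follow-up". The follow-up survey takes place three weeks after post-intervention.

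The other follow-up content listed in the Protocol is attention checks, the condition guess, and optional questions on participants' "perspectives and overall experience of the protocol (post-intervention) / study-period (follow-up". Adherence, item 10, is also recorded once: "number of sessions participants self-report practicing out of 21 days assigned). Measured post-intervention".

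In the SAP, negative effects fall under the heading "Exploratory analysis of secondary measures". The entry asks whether each kind of effect was experienced and ends: "Lasting bad effects from the breathwork. Analysis will be content analysis". Under the same heading, adherence and CEQ-6 scores are compared between groups by unpaired t-test. Earlier, the SAP promises descriptive statistics for all measures in each condition. It names sentiment analysis for the experience answers at post-intervention only.

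**The concern.** The Protocol's Background makes safety one of the reasons for the trial. It says the safety profile of fast breathwork needs more research, notes that only six of the 26 studies in the sponsor's meta-analysis actively reported negative effects, and undertakes to report them here. Two features of the plan limit what that report can say.

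- **Timing.** An effect that began in week 1 and was still present at post-intervention can be reported as lasting. Whether it outlived the practice period, cleared up, or first appeared in the next three weeks is not asked, although a survey already reaches participants then.
- **Analysis.** Some discomfort may also be reported with paced breathing and short breath-holds. The placebo arm makes it possible to estimate how many more participants report negative effects under HVBR, and with what uncertainty. Content analysis yields themes and does not give that estimate.

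**Working it through.** **What each survey covers, from the two documents**

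| Content | Post-intervention | Three-week follow-up |
|---|---|---|
| Stress, anxiety, depression, wellbeing, sleep | yes, compared by arm | yes, compared by arm |
| Negative effects, short-term and lasting | yes, content analysis | not listed |
| Experience questions | optional, sentiment analysis | optional, no method named |
| Adherence | yes, t-test | not listed |
| Condition guess | not listed | yes, at the end |

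The gap at follow-up is thus confined to effects outside the five scales and effects that participants attribute to the breathwork.

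**Inputs.** The planned size is 200, 100 per arm (Protocol, Participants). The documents give no negative-effect rate and no attrition rate, so every count below, and the denominators of 85 and 70, are assumptions. There is no stated figure for this outcome to reproduce. The Protocol's requirement for the primary comparison (standardised effect 0.50, power 0.80, significance level 0.05) does reproduce: a two-sided two-sample t-test needs 63.77, hence 64 per arm and 128 in all.

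**Risk difference with Newcombe 95% interval.** Let p1 and p2 be the observed proportions (HVBR, placebo), with Wilson limits (l1, u1) and (l2, u2), and d = p1 - p2.

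- Lower limit = d - √[(p1 - l1)² + (u2 - p2)²]
- Upper limit = d + √[(u1 - p1)² + (p2 - l2)²]

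Worked case, 10/100 against 5/100. The Wilson limits are 0.0552 to 0.1744 and 0.0215 to 0.1118.

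- Lower: 0.05 - √(0.0448² + 0.0618²) = 0.05 - 0.076 = -0.026
- Upper: 0.05 + √(0.0744² + 0.0285²) = 0.05 + 0.080 = 0.130

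| Assumed counts, HVBR and placebo | Difference | 95% interval |
|---|---|---|
| 5/100 and 5/100 | 0.000 | -0.068 to 0.068 |
| 10/100 and 5/100 | 0.050 | -0.026 to 0.130 |
| 20/100 and 8/100 | 0.120 | 0.023 to 0.217 |
| 17/85 and 7/85 | 0.118 | 0.012 to 0.223 |

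**Chance that the interval excludes zero.** Summing exact binomial probabilities over all pairs of counts at 100 per arm gives 0.238 for true rates of 10% and 5%, and 0.702 for 20% and 8%. The interval is an estimate and should not be presented as a dependable test.

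**No lasting effects reported in an arm.** The one-sided 95% upper bound is 1 - 0.05^(1/n): 3.0% at n = 100, 3.5% at n = 85, 4.2% at n = 70. Silence from one arm would still be compatible with a true rate of about 3% to 4%.

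All these figures bear on the analysis half of the point. The documents offer no basis for quantifying what a repeat at follow-up would add.

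**The case against.** The strongest reply is that nothing here is an error. The Protocol says that participants will be asked about short- and long-term negative effects, and asking once satisfies that wording. A reader might infer that the documents contradict themselves; they do not.

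A reader might also infer that follow-up is blind to harm. It is not: items 1 to 5 are measured then and compared between arms, so group-level deterioration in stress, mood, wellbeing or sleep would be picked up without anyone volunteering it. Nor do the documents say that the item is answered on the very day practice stops. They place it three weeks after randomisation and give no completion window.

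On the analysis, the promise of descriptive statistics by condition may well cover this item, and a reader with two counts and two denominators could compute the interval. The t-tests for adherence and CEQ-6 are an imperfect comparison, because those are numeric scores. The questionnaire is not in the documents, so a clean yes/no answer is inferred from the SAP's phrasing.

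These replies stand and narrow the point. What remains is that no between-arm estimate is committed to, that reporting the counts and their denominators is not explicit, and that self-attributed or physical effects after post-intervention are left to optional open questions.

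A repeat at follow-up has its own weakness. If it comes before the condition guess it may cue the guess; if after, the guess may colour the answers.

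**Conclusion.** The point holds as an inexpensive improvement to a secondary safety outcome. Followed as written, the plan makes no dedicated harms enquiry after post-intervention and commits to no between-arm difference or interval for the one it makes. The primary outcome and its analysis are untouched.

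The benefit is a stated range. Under the assumed 10 and 5 events per 100, the report could say that the excess under HVBR is unlikely to be above about 13 points, though it could not exclude no excess. The size rests on assumed counts and on the item yielding a yes/no answer per participant.

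One further inference should be resisted: that asking about continued practice would let the trial separate persisting effects from those of further sessions. No passage says that access ends after day 21; of the audio the Protocol says only "This will be delivered remotely online through audio link". Continuing is therefore possible, but it is a self-selected behaviour after randomisation, and those with bad effects may be the ones who stop. A split on it can only describe.

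**What to change.** 1. **SAP, Negative side effects.** Report by arm the number and percentage with any short-term and with any lasting effect, the number not answering the item, and the risk difference with a 95% interval (Newcombe, for example). Label it an estimate and not a powered test. Keep content analysis for the free text, coded with arm labels removed.
2. **Follow-up survey.** Repeat the item, placed after the condition guess so that it does not cue the guess. Treat the by-arm comparison at follow-up as descriptive, because the guess may colour answers. A short question on practice after day 21 may be added, for description only.

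The cost is a few lines of SAP text and one repeated item, or two short items with the optional practice question, in a survey that already runs. The downsides are a slightly longer survey, some prompting of reports (perhaps unequal between arms), and answers influenced by the guess. Reporting the number not answering discloses non-response but does not remove any bias from it.

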Study Protocol

Effects of high ventilation breathwork with retention on mental health and wellbeing: A randomised placebo-controlled trial (NCT06064474)

[name], [name], [name], [name], [name]

Document date: October 09, 2023

Background & rationale

There has been an unprecedented surge in public/scientific interest in a style of breathwork that incorporates hyperventilation (high ventilation) with breath-holds (retention). This technique has similarities to Tibetan Tummo meditation and Yogic Pranayama but has been popularised in the West by the Wim Hof Method (Kox et al., 2014). Despite emerging research there are no well-controlled studies exploring effects of high ventilation breathwork with retention (HVBR) on mental health and wellbeing. We plan to complete the first robust randomised-controlled trial (RCT) comparing HVBR (20 minutes/day) for three weeks to a well-designed placebo (paced breathing at 15 breaths/min with retentions). The metric of 15b/min aligns with guidance from the British Journal of Nursing, Royal College of Physicians and Johns Hopkins Medicine which state that the average, healthy rate should range from: 12-20, 12-18 and 12-16b/min, respectively.

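### The study name 'Sussex Fast Breathwork Study' fits only the hyperventilation arm and may cue control participants to their allocation, in a trial whose scale outcomes are all self-rated

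*Protocol*

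**What the plan says.** The Protocol (Randomisation & blinding) describes two blinding devices in one sentence. First, "the study is referred to as the Sussex Fast Breathwork Study". Second, the technique "will be referred to as 'rhythmic breathing' in both the active intervention and placebo control breathwork audios". Both are offered "in an attempt to blind participants to the intervention being used".

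Under Intervention & Comparator, the active audio has "four rounds of hyperventilation with four separate retentions (breath holds), progressively increasing in length", from about 45 to about 90 seconds. The control audio has "four rounds of paced breathing at 15b/min (equal inhale:exhale without pauses", and "four separate (shorter) retentions, slightly increasing in length (from ~10secs to ~25secs". Both run for about 20 minutes with music and four rounds. Background & rationale justifies the control rate by citing three sources that "state that the average, healthy rate should range from: 12-20, 12-18 and 12-16b/min, respectively".

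The Procedure says that people see a title and a description of what they will do before they join. Under Participants, entrants must confirm that they are at ease with holding the breath and with breathing faster. Outcome measures and Randomisation & blinding make clear that participants complete every questionnaire themselves online, including the primary DASS-21 stress subscale.

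Two checks are planned. The CEQ-6 (credibility and expectancy) is completed after the first session and compared between arms. If the arms differ significantly, the SAP re-runs the primary tests with it as a covariate. Participants are also asked to guess their condition at the end of the follow-up questionnaire.

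**The concern.** The two blinding devices pull in different directions. 'Rhythmic breathing' describes either audio equally well. 'Fast Breathwork' describes only one of them. A control participant who has joined a study with that name, has confirmed being comfortable with faster breathing, and is then paced at an ordinary rate has a reason to wonder whether this is the technique under study. An HVBR participant gets what the name promised.

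This matters because participant blinding is the only blinding that protects the outcomes. The assessor blinding means only that no assessor is present, so the participant is the assessor. Background & rationale criticises two earlier trials for having no placebo, because specific effects could not then be separated from attention and expectation, and it aims for the first fast-breathwork trial at low risk of bias. If expectancy differs between arms because of the study's own label, that difference can enter the self-rated stress score and look like a treatment effect.

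**Working it through.** **1. Does each label fit each arm?**

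| Element | HVBR | Control |
|---|---|---|
| Breathing | hyperventilation | 15 breaths/min, paced |
| Holds | four, about 45 to 90 s | four, about 10 to 25 s |
| Fits 'Fast Breathwork' | yes | no, by the Protocol's own ranges |
| Fits 'rhythmic breathing' | yes | yes |

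The three cited ranges are 12-20, 12-18 and 12-16 breaths/min. Background & rationale and Intervention & Comparator assign the first two to different sources, but 15 lies inside all three, so this does not affect the point.

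**2. Do participants see the name?** The Prolific title and description are not in the documents. The name can serve blinding only if participants meet it, and the Procedure says they see a title before joining. I take it as participant-facing on that basis.

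**3. The plan's own figure.** The Protocol asks for 128 participants (64 per group) for an effect of 0.50, power 0.80 and significance level 0.05. The two-sided normal approximation gives n = 2(1.96 + 0.84)²/0.50² ≈ 62.7, so 63 per arm and 126 in total. The two-sample t-test gives 63.77, so 64 per arm and 128 in total. The stated figure reproduces. With the planned 100 per arm, power for 0.50 SD is 94%. The sample size is not at issue here, but it gives the scale on which to judge a bias.

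**4. What a bias would do.** The documents give no rate of unblinding and no size for its effect, so both inputs below are assumptions:
- share of controls who infer their arm, p: 0.25 to 0.75
- shift in their self-rated stress, s: 0.2 to 0.4 SD, with no shift in the HVBR arm

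Bias b = p × s. With n = 100 per arm and no true effect, the standardised shift is b × √(n/2) = b × √50 = 7.07b, and the false-positive rate is P(|Z + 7.07b| > 1.96).

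| p × s | b (SD) | b / 0.50 | 7.07b | False-positive rate |
|---|---|---|---|---|
| 0.25 × 0.2 | 0.05 | 10% | 0.35 | about 6% |
| 0.50 × 0.3 | 0.15 | 30% | 1.06 | about 19% |
| 0.75 × 0.4 | 0.30 | 60% | 2.12 | about 56% |

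A t-test calculation also gives 56% at 0.30 SD. With 64 per arm it gives about 39%, so a larger sample makes a fixed bias more likely to reach significance. This is a simple two-group comparison and not the planned baseline-adjusted mixed ANOVA, so the rates are approximate.

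**5. What the table does not show.** It describes unblinding from any source. The study name, the eligibility wording, the pre-enrolment description and the audio itself could all contribute. The share due to the name alone cannot be derived from the documents and may be small.

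**The case against.** The strongest case on the other side has four parts.

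- **The name is the same for everyone and is met before randomisation.** No passage says that participants are told their breathing rate, the normal range or what the other arm does. The ranges are rationale in the Protocol, not participant information. The sham shares the music, the four rounds and the lengthening holds, and continuous pacing at 15 breaths/min is above the lower end of the cited ranges. The name may even have been meant to let the sham pass as fast breathwork. This stands as a limit on how far the point goes. A reader might infer that the name reveals the control allocation. The documents do not support that: whether participants would notice the mismatch is an empirical question they leave open. A shared name is still not a neutral one when only one arm fits it.

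- **The plan already checks for this.** The CEQ-6 is taken at about the time a control participant would first notice, and the allocation guess asks directly. Both deserve credit, but they detect and do not prevent. The covariate re-run depends on a significant difference, and it adjusts for a variable measured after randomisation that may itself reflect the session. The guess comes three weeks after the primary timepoint, when perceived benefit can colour it, and the SAP specifies no analysis for it.

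- **The eligibility item stays.** Entrants will still be asked about faster breathing whatever the study is called. That is so, and it means a new name removes one cue among several. It is not a reason to keep a cue that no safety purpose requires.

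- **The direction is assumed.** That is fair. A bias in favour of HVBR is the likelier direction, because the name raises an expectation that only that arm meets, but the documents contain no evidence on it.

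**Conclusion.** The point holds as a risk, not as a demonstrated failure of blinding. By the Protocol's own account the name used for blinding fits one arm and not the other, and together with the eligibility item it may cue control participants to their allocation and lower their expectancy. All scale outcomes, including primary stress, are self-rated, so a resulting bias would probably favour HVBR.

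The size is unknown. The range of about 6% to 56% rests on assumed biases of 0.05 to 0.30 SD with 100 per arm, no true effect and no shift in the HVBR arm. A reader might take that range as the effect of the name, or as what renaming would remove. It is neither: it shows how sensitive the primary comparison is to unblinding in general. The conclusion also assumes that the name appears in the participant materials, which are not in the documents.

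The change is worth making because the cue is avoidable and the remedy is cheap, not because a large bias has been shown.

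**What to change.** Use a participant-facing name that fits both arms and matches the label already in the audios, for example 'Sussex Rhythmic Breathing Study'. Apply it throughout: Prolific title and description, surveys, daily reminders and audio recordings. Leave the safety eligibility items and the consent information on faster breathing and breath-holds unchanged, and amend the sentence on the study name under Randomisation & blinding.

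The cost is a wording change and a minor ethics notification, with no effect on sample size or analysis. The eligibility wording will still leave some cueing.

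If recruitment has already begun under the present name, a partial remedy is to ask for the allocation guess, with reasons, after the outcome scales in the post-intervention survey, and to pre-specify a blinding index in the SAP. That would measure the problem nearer the primary timepoint but would not prevent it.
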